11.0 Local Recruitment Methods

11.1 Recruitment Process: Participants will be recruited from the MHealth Clinics and Surgery Center. The PI or research assistant (RA) will be notified by BPIC 3-5 days prior to a potential recruit's visit to orthopedics. The PI will confirm eligibility through reviewing the EMR. The PI/RA, as Nonemployee Research Staff (NERS), have approved access to such. The study orthopedist will be informed of the client's eligibility by the PI/RA and who will then briefly present the study and ask the patient for permission for the PI or study staff to present the study to them in more depth during their clinic visit. If interested, the informed consent process will follow.

If recruitment efforts through these methods are slow, potential participants will also be identified in the i2b2 database then run by BPIC and sent to Fairview for mail-invitation. Alternatively, Fairview's Research Recruitment services may perform the same service. These letters or MyChart Messages will be sent to those who qualify via the Fairview Recruitment Mailing Service. Patients will then outreach to the PI for additional details and, if interested, will proceed with the informed consent process.

After which, the initial assessment and subsequent therapy sessions will be scheduled. We will use selective stratified sampling to enroll equal numbers of persons with baseline Eaton³⁰ thumb CMC OA stages 1, 2, and 3 respectively (i.e., 16-17 participants per strata). The study will be closed to recruitment for those of a strata which has achieved 16-17 participants.

MEDICAL PROTOCOL (HRP-590)

PROTOCOL TITLE: Mechanisms of a Dynamic Stability Approach

VERSION DATE: 05/25/2023

Successful recruitment appears feasible given the findings of a recent analysis of Fairview/UHealth dataset through use of the University of Minnesota CTSI's "i2b2 Cohort Discovery tool." The survey of our participant pool revealed that 4,858 persons (3363 women and 1495 men) who met the inclusion criteria for participation were seen in Fairview/UHealth Sports and Orthopaedic Clinics from January 1st, 2018 to March 11th, 2021.

Although the prevalence of radiographically confirmed thumb CMC OA is similar in men and women²⁷, our survey of our participant pool appears to reveal a care-seeking gender discrepancy. This discrepancy is consistent with the findings of health service research²⁸ and thus, while evidence suggests that women and men are affected equally by this condition, we anticipate that the population from which we will recruit will be disproportionately female and, in a study of this nature, we will not attempt to selectively recruit men.

In being consistent with the demographics of Minneapolis we will aim to recruit the following racial distribution: White: 64%, Black or African American: 19%, Asian: 6%, other: 5%, multiracial 5%, and Native American: 1%. Thus we will work to selectively recruit approximately 30 white, 9 African American, 5 Latino American, and 5 Asian American participants. If this diversity is not met through recruitment on a rolling basis, we will work with BPIC to identify those who meet these criteria and selectively recruit these persons.

11.2 Identification of Potential Participants: The PI or research assistant (RA) will be notified by BPIC 3-5 days prior to a potential recruit's visit to orthopedics. The PI will confirm eligibility through reviewing the EMR. The PI/RA, as Nonemployee Research Staff (NERS), have approved access to such. The study orthopedist will be informed of the client's eligibility by the PI/RA and who will then briefly present the study and ask the patient for permission for the PI or study staff to present the study to them in more depth during their clinic visit.

If recruitment efforts through these methods are slow, potential participants will also be identified in the i2b2 database then run by BPIC and sent to Fairview for mail-invitation. Alternatively, Fairview's Research Recruitment services may perform the same service. These letters or MyChart Messages will be sent to those who qualify via the Fairview Recruitment Mailing Service

11.3 Recruitment Materials: Recruitment materials will include a brief description of the study. This will be provided at the time of the initial encounter with the surgeon. Please see the Participant handout provided in the ETHOS application.

If using health records to identify potential participants, an IRB and Fairview Research Administration approved letter will be mailed or sent via MyChart.

11.4 Payment: Greenphire ClinCards will be given to each participant to compensate for time and parking expenses. Cards will be loaded with a reimbursement of \$25.00 after attending each study-associated therapy and evaluation session (6 sessions x 25.00 = 150.00). Additionally, \$6.00 per visit will be provided for parking for 6 visits (6 x \$6.00 = 36.00). In total, participants will receive compensation for attending 4 therapy-only visits, and 2 evaluation-only visits (i.e., baseline, and 9-week follow-ups). Should participants continue with therapy beyond the study period, the remaining therapy costs will be billed to participants' health insurance in the typical fashion. The maximum compensation amount for each participant would be \$186.00.

12.0 Withdrawal of Participants

MEDICAL PROTOCOL (HRP-590)

PROTOCOL TITLE: Mechanisms of a Dynamic Stability Approach

VERSION DATE: 05/25/2023

12.1 Withdrawal Circumstances:

An investigator may discontinue a participant from the study for the following reasons:

- Significant study intervention non-compliance
- If any clinical adverse event (AE), laboratory abnormality, or other medical condition or situation occurs such that continued participation in the study would not be in the best interest of the participant
- If the participant meets an exclusion criterion (either newly developed or not previously recognized) that precludes further study participation
- If they are lost to follow up
- If they behave inappropriately toward study staff
- Disease progression which requires discontinuation of the study intervention
- If they show signs of diminished capacity to consent
- Or it is in their best interest, as determined by the PI

Recruits will be informed that participation in this study is voluntary. They will be informed that their decision on whether or not to participate in this study will not affect their current or future relations with the University, University of Minnesota Medical Center, or Fairview. Recruits will be informed that, if they decide to participate, they are free to withdraw at any time without affecting those relationships.

12.2 Withdrawal Procedures: If participants choose to withdraw from the study, data collection will be discontinued with no further follow up. Participants who are withdrawing from the study will be asked to consider providing consent for subsequent data collection to follow up on their medical outcomes related to the project. Thus, participants will be presented with the option to sign a "Consent Collection after Withdrawal" to enable this future data collection. All data collected up to the point of participant withdrawal from the study will continue to be securely stored and analyzed. Primary and secondary outcomes will be handled through intent to treat analysis. Records will be kept on number of withdrawals as well as the reasoning for such.

12.3 Termination Procedures: This study may be temporarily suspended or prematurely terminated if there is sufficient reasonable cause. Written notification, documenting the reason for study suspension or termination, will be provided by the suspending or terminating party to the funding agency, and regulatory authorities. If the study is prematurely terminated or suspended, the PI will promptly inform the IRB and will provide the reason(s) for the termination or suspension. The study team will notify the participants of the study termination.

Circumstances that may warrant termination or suspension include, but are not limited to:

- Determination of unexpected, significant, or unacceptable risk to participants
- Insufficient compliance to protocol requirements
- Data that are not sufficiently complete and/or evaluable
- Determination that the primary endpoint has been met
- Determination of futility

Records will be kept on number of withdrawals as well as the reasoning for such.

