19.0 Provisions to Protect the Privacy Interests of Participants

19.1 Protecting Privacy: Information about study subjects will be kept confidential and managed according to the requirements of the Health Insurance Portability and Accountability Act of 1996 (HIPAA). Those regulations require a signed subject authorization informing the subject of the following:

- What protected health information (PHI) will be collected from subjects in this study
- Who will have access to that information and why
- Who will use or disclose that information
- The rights of a research subject to revoke their authorization for use of their PHI.

In the event that a subject revokes authorization to collect or use PHI, the investigator, by regulation, retains the ability to use all information collected prior to the revocation of subject authorization. For subjects that have revoked authorization to collect or use PHI, attempts should be made to obtain permission to collect at least vital status (i.e. that the subject is alive) at the end of their scheduled study period.

Participants who are withdrawing from the study will be asked to consider providing consent for subsequent data collection to follow up on their medical outcomes related to the project. Thus, participants will be presented with the option to sign a “Consent Collection after Withdrawal” to enable this future data collection.

19.2 Access to Participants: Participants will be fully informed of the ways in which their data will/may be used during the informed consent process. The research team has been trained in conducting these conversations and the participants are also assessed for their understanding of consent prior to initiating any study procedures.

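### Section 12.1 allows removal from the study for non-adherence or progression while 12.2 promises intent to treat, and the protocol does not say whether those removed are still assessed at week 9

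*Combined protocol and SAP*

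**What the plan says.** Section 12.1 opens: "An investigator may discontinue a participant from the study for the following reasons". The list includes "Significant study intervention non-compliance", with no threshold for what counts as significant, and "Disease progression which requires discontinuation of the study intervention". In both cases the participant leaves the study, not just the exercise programme.

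Section 12.2 then makes three statements that bear on outcomes:
- "If participants choose to withdraw from the study, data collection will be discontinued with no further follow up". This is worded for participants who decide to leave.
- Those who are withdrawing are asked to consider giving "consent for subsequent data collection to follow up on their medical outcomes related to the project". Section 19.1 repeats this: "Participants who are withdrawing from the study will be asked to consider providing consent for subsequent data collection".
- "Primary and secondary outcomes will be handled through intent to treat analysis".

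Section 5.1 names week 9 as the primary follow-up. The schedule in Section 5.2 shows CT, ultrasound and the Michigan Hand Questionnaire at baseline and week 9 only. (Section 3.1 also mentions 6 and 12 weeks for the primary outcome. The schedule has no such assessments, and the two need reconciling.) Section 15.1 analyses mean change from baseline to week 9, with regression on arthritis stage. It defines no analysis set and gives no rule for a missing week-9 CT. Section 15.3 only refers back to 15.1.

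**The concern.** Under intent to treat, adherence does not decide who is analysed. A rule that allows removal from the study for poor adherence works against that, because the outcome is measured only once after treatment. Anyone not seen at week 9 has a baseline value and no change score. The sentence in 12.2 that data collected before withdrawal will still be analysed cannot supply one.

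Aim 1 is to describe the change in subluxation, so the mean change is itself the result. Non-adherence and progression are plausibly related to how much an exercise programme achieves. If people removed for those reasons are not scanned, the reported mean describes those who stayed, and there is no comparison arm in which the same selection would show up. The disability change collected under Aim 1b for planning a later comparative trial has the same gap. The stage adjustment does not address it, and the 20% allowance for loss to follow-up protects precision, not against selection.

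**Working it through.** **The plan's own figure.** Inputs from Section 15.2: sustained change 0.15 cm, SD of one measurement 0.22 cm, pre-post correlation 0.2, two-sided alpha 0.05, power 90%, 20% loss.

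- SD of change = 0.22 × √(2 × (1 − 0.2)) = 0.278 cm.
- Paired t-test, noncentral t: n = 38 gives power 0.899 and n = 39 gives 0.907, so 39 pairs. 39 / 0.8 = 48.75, so 49 enrolled. The stated 39 and 49 reproduce, so the sample size is not at fault.
- Planned standard error = 0.278 / √39 = 0.0446 cm.

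**What selection could do.** The documents give no removal rate and no outcomes in those removed, so m (number removed) and e (their mean change) are assumptions. Completers are set at the plan's 0.15 cm.

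All-enrolled mean = ((49 − m) × 0.15 + m × e) / 49. Overstatement = 0.15 / (all-enrolled mean) − 1.

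| m | e (cm) | All-enrolled mean (cm) | Shift (cm) | Overstatement |
|---|---|---|---|---|
| 2 or 5 | 0.15 | 0.150 | 0 | 0% |
| 2 | 0.075 | 0.147 | 0.003 | 2.1% |
| 2 | 0 | 0.144 | 0.006 | 4.3% |
| 2 | −0.075 | 0.141 | 0.009 | 6.5% |
| 5 | 0.075 | 0.142 | 0.008 | 5.4% |
| 5 | 0 | 0.135 | 0.015 | 11.4% |
| 5 | −0.075 | 0.127 | 0.023 | 18.1% |

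Worked example, last row: (44 × 0.15 + 5 × (−0.075)) / 49 = 6.225 / 49 = 0.127, and 0.15 / 0.127 − 1 = 18.1%. The shift of 0.023 cm is 0.52 of the planned standard error. With 44 completers the standard error is 0.278 / √44 = 0.042 cm, and the ratio is 0.55. Zero is not a floor for e, because participants who progress could worsen.

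**Effect on the test if the removed are measured.** Take m = 5, p = 5/49, and SD of the mixture = √(0.278² + p(1 − p)(0.15 − e)²). Approximate power with all 49:

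| e (cm) | t | Power |
|---|---|---|
| 0.15 | 3.77 | 0.96 |
| 0.075 | 3.57 | 0.94 |
| 0 | 3.34 | 0.91 |
| −0.075 | 3.10 | 0.86 |

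For 44 completers alone, t is 3.58 and power 0.94. Measuring those removed can therefore raise or lower power, with the break-even at about half the planned effect.

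**The case against.** The strongest reply is that nothing in the protocol says week-9 assessment stops for someone the investigator removes. A reader might infer from 12.1 and 12.2 together that such a participant necessarily has no change score. The text does not go that far: the sentence ending follow-up covers only those who choose to leave, and the sentence on later data collection can be read to include those removed. This objection stands. What remains is that being discontinued from the study makes a further study visit doubtful, no passage commits to one, and the data-collection option is voluntary and, in the protocol text, does not mention the week-9 CT. The separate consent form is not among the documents reviewed, so no fault can be found with it. Its wording may already be broader.

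It is also fair that removal is discretionary, that reasons for withdrawal and exercise logs are kept so selection would be partly visible, and that the primary calculation would in practice use the same paired values. These points limit the harm. They do not recover a CT that was never taken.

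A reader might also take the whole 20% loss allowance as the measure of bias. Ten lost at zero change would give 39 × 0.15 / 49 = 0.119 cm, an overstatement of 26%. That treats every loss as a zero-effect removal, which no passage supports, and clearer removal wording would not recover most ordinary losses. That figure should not drive the judgement.

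**Conclusion.** The point holds as a conflict between a removal rule and an analysis promise, left open by silence on follow-up after investigator removal and on missing week-9 CTs. It is not a demonstrated bias. If removal ends assessment, the mean change may be selected on adherence. Under the assumed 2 to 5 removals, with a mean change in them from 0.15 cm down to −0.075 cm, the overstatement is 0% to 18%, at most 0.023 cm or about half a standard error. It is nil if those removed change as completers do. The real frequency of removal and the outcomes in those removed are unknown, so the direction is plausible and the size is modest and assumed. It should be fixed because the change is cheap and a missed CT cannot be obtained later.

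**What to change.** In Sections 12.1 and 12.2:
- Separate stopping or not following the exercise programme from leaving the study. State that non-compliance or stopping the intervention does not by itself end outcome collection.
- Seek the already scheduled week-9 CT, ultrasound and questionnaire in these participants where consent continues and no safety reason or exclusion applies. Treatment and safety decisions stay with the clinical team.
- Make clear in the protocol text that the option of data collection after withdrawal also applies after removal by the investigator and includes the week-9 assessments.

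In Section 15.1:
- Analyse every enrolled participant with a baseline and a week-9 CT, regardless of adherence. Describe the set that way, and do not call it full intent to treat if CTs are missing.
- Report the number of missing week-9 CTs and the reasons.
- Add a simple sensitivity analysis over assumed mean changes in those missing, from the completer mean through zero to worsening.

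The cost is protocol wording and one extra analysis, since the visits are already scheduled. The downsides are the effort of bringing back non-adherers, a possibly smaller mean change, and slightly lower power if those recovered have less than about half the planned effect.

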15.0 Statistical Considerations

MEDICAL PROTOCOL (HRP-590)

PROTOCOL TITLE: Mechanisms of a Dynamic Stability Approach

VERSION DATE: 05/25/2023

15.1 Data Analysis Plan: For aim #1, the within-subjects outcomes will be compared primarily on the mean change in degree of subluxation from baseline to 9 week follow-up (the primary outcome). Additionally, given our recent retrospective findings²⁷ which support that advanced arthritic radiographic staging is also a negative predictor of response to the DS, mean change scores will be compared and adjusted for according to arthritic staging through use of linear regression for added precision of the treatment effect estimates. For aim #2, the agreement between baseline radial subluxation measurements via CT measurements and those via sonography will be assessed using the Bland-Altman method.⁴²

15.2 Power Analysis:

Aim #1: Previous work⁸ suggested that the mean immediate misalignment change in the treatment group will be 0.33 cm, with a standard deviation of 0.18. The proposed sample size was estimated a priori assuming a paired t-test of the change in misalignment, with two-tailed type I error of 0.05 and power of 90%. We conservatively estimate that the minimum clinically important change in misalignment will be between 0.05cm and 0.40cm, depending on how much the sustained effect is attenuated relative to the immediate effect (published value 0.42cm), and that the standard deviation (SD) of the misalignment measurement is 0.22cm. The correlation between the pre and post measurements is unknown, so we estimate the needed sample size for a range of correlation values between 0.20 and 0.80.

If we conservatively assume that the immediate misalignment change is 0.30cm, that the sustained change will be reduced by 50% to 0.15cm, and that the pre and post measurements will only be weakly correlated with a correlation coefficient of 0.2, then a sample size of 39 people (39 pre and post measurements) will be required. Assuming a potential loss-to-follow-up rate of 20%, we will enroll 49 participants.

Aim #2: A formal sample size estimate is not available for this aim given its novelty. However, because a sample of 30 participants is assumed to be adequate for bivariate correlational research³⁷, we anticipate that our sample of 49 participants will be adequately powered.

15.3 Statistical Analysis: See section 15.1.

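### Section 12.2 promises intent to treat, but the change-score analysis in 15.1 and 15.2 can use only participants scanned at both visits, and nothing says how a missing week-9 CT is handled

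*Combined protocol and SAP*

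**What the plan says.** **Withdrawal (12.2).** By default follow-up stops: "If participants choose to withdraw from the study, data collection will be discontinued with no further follow up". Participants who withdraw are offered a separate consent to later data collection, but a week-9 CT is not named there. Two commitments follow: "All data collected up to the point of participant withdrawal from the study will continue to be securely stored and analyzed", and "Primary and secondary outcomes will be handled through intent to treat analysis". Intent to treat is not defined.

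**Analysis (15.1).** For Aim 1, "the within-subjects outcomes will be compared primarily on the mean change in degree of subluxation from baseline to 9 week follow-up". In addition, "mean change scores will be compared and adjusted for according to arthritic staging through use of linear regression". Baseline subluxation is not a covariate. Section 15.3 only points back to 15.1.

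**Sample size (15.2).** "The proposed sample size was estimated a priori assuming a paired t-test of the change in misalignment". The result is 39 people, each with a pre and a post measurement. Then: "Assuming a potential loss-to-follow-up rate of 20%, we will enroll 49 participants".

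**Measurement (5.2).** The assessment table shows CT at baseline and week 9 only. Subluxation is not measured until participants have completed the 8-week protocol. The baseline and week-9 films are then read in random order.

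**The concern.** A change score needs two scans. A participant lost before week 9 has one scan and no intermediate value, so neither a mean change, nor a change-score regression on stage, nor a paired t-test can include that person. The plan expects this for about 10 of 49 (20% of 49 = 9.8). The intent-to-treat promise therefore has no method behind it, and the promise to analyse data collected before withdrawal is not kept for the primary outcome. The reading rule in 5.2 points the same way, because it gives no time at which the baseline scan of someone who never completes is measured.

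Enrolling 49 to keep 39 protects power but does nothing about bias. If those lost differ at baseline from those who stay, the completers' mean change is not the mean change of the people enrolled. With no rule written down, how to treat those without a week-9 scan could be decided after the data are seen.

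**Working it through.** **Inputs from 15.2.** SD of one measurement 0.22 cm; sustained change 0.15 cm, taken here as a reduction (baseline minus week 9); correlation r = 0.2, from a stated range of 0.20 to 0.80; two-sided alpha 0.05; power 90%; loss 20%. The loss mechanism is not in the documents and is assumed below.

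**1. The plan's own figure.** SD of change = 0.22 × √(2 × (1 − 0.2)) = 0.2783 cm. The exact paired t-test needs n = 39 (power 90.7%), and 39 / 0.80 = 48.75, so 49. Both figures reproduce. The 39 are complete pairs and 49 − 39 = 10 are not.

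**2. Precision.**
- Complete pairs: SE = 0.22 × √(2(1 − r)/39).
- Two-visit likelihood model with all 49 baselines: SE = 0.22 × √((1 − r²)/39 + (1 − r)²/49).

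| r | Pairs, SE (cm) | Model, SE (cm) | Reduction |
|---|---|---|---|
| 0.2 | 0.0446 | 0.0427 | 4.2% |
| 0.5 | 0.0352 | 0.0343 | 2.6% |
| 0.8 | 0.0223 | 0.0221 | 1.0% |

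The precision gain is small.

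**3. Bias if loss depends on baseline.** With equal SDs at both visits, the slope of post-minus-pre change on baseline is r − 1, which is −0.8 at r = 0.2. If those lost start g baseline SDs above those who stay, the bias in the completers' mean reduction is

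bias = −(1 − r) × (10/49) × g × 0.22 cm.

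Simulation: 10 of 49 are lost, with the weight of being lost multiplied by w for each baseline SD (40,000 trials per case). w = 1.5 gives g of about 0.44, and w = e gives g of about 0.96. At r = 0.2 and g = 0.96: −0.8 × 0.2041 × 0.96 × 0.22 = −0.0345 cm, which leaves about 0.116 cm.

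| r | Random loss | w = 1.5 | w = e | Model, all cases |
|---|---|---|---|---|
| 0.2 | 0.150 | 0.134 | 0.116 | 0.150 |
| 0.5 | 0.150 | 0.140 | 0.128 | 0.150 |
| 0.8 | 0.150 | 0.146 | 0.141 | 0.150 |

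The first three columns of results are the completers' mean in cm; the true value is 0.150. At r = 0.2, the 95% CI coverage of the completers' analysis falls to 94% (w = 1.5) and 87% (w = e), and power falls to 84% and 74%. If low baselines are lost instead, the sign reverses: about 0.166 and 0.184 cm at r = 0.2.

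**4. Where the model does not help.** If loss depends on the unobserved week-9 value (weight 2 per SD, r = 0.2), the completers' mean is 0.176 cm and the model gives 0.181 cm. Both are biased, the model slightly more.

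**The case against.** - **Complete pairs are inferred.** A reader might infer that the plan prescribes a complete-pair analysis and so contains two conflicting written rules. It does not say so. The paired t-test appears only as a sizing device in 15.2, inflating for loss is routine, and 12.2 leaves intent to treat undefined; in a single-arm study the term could simply mean analysing people regardless of adherence. What stands is one undefined promise, a method that needs both scans, and silence on the rest.
- **Some withdrawers could still be scanned.** The optional consent in 12.2 makes this possible, so it is too strong to say that nobody who leaves can have a change score. It does not help with those truly lost.
- **The bias is conditional.** A reader might infer that the result will be understated by 0.035 cm. That is the largest of the cases above, at the lowest correlation the plan considers. The documents give no dropout pattern; random loss gives no bias, and the direction is unknown.
- **Carrying the baseline forward is not in the plan.** It should not be read as the plan's meaning of intent to treat.
- **The comparison in step 3 suits the model.** Loss there depends only on baseline, the condition under which the model is unbiased. Several removal reasons in 12.1 (non-compliance, adverse events, disease progression) arise after baseline. This stands, and it is why a sensitivity analysis is needed.
- **Stage adjustment may help.** It removes only the part of the dependence that runs through Eaton stage, and only if the mean is standardised to the enrolled stage mix. It still needs a change score.

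**Conclusion.** The concern holds: 12.2 promises an intent-to-treat analysis that the method in 15.1 and 15.2 cannot deliver for participants without a week-9 CT, and no missing-data rule fills the gap. With random loss the completers' mean is unbiased. With baseline-related loss in the assumed range of 1.5 to e per SD, the bias is about 0.016 to 0.034 cm at r = 0.2 and 0.004 to 0.009 cm at r = 0.8, against an assumed effect of 0.15 cm, with the sign set by which participants leave. These sizes rest on equal SDs at the two visits, 10 of 49 lost, and loss mechanisms that the documents neither support nor exclude. The unused baseline scans cost little precision (1 to 4% of the SE); the reasons to change are bias and pre-specification. It should be settled before the analysis, but it does not invalidate the design or the sample size.

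**What to change.** **15.1.** Make the primary analysis a two-visit likelihood-based model (REML, unstructured covariance) that includes every enrolled participant with a baseline CT. The estimate is the week-9 minus baseline contrast with its 95% CI. Keep the Eaton-stage adjustment through stage and stage-by-visit terms, averaged over the enrolled stage mix. The model needs one subluxation value per participant per visit. Section 5.2 takes four images per affected hand, and both hands if bilateral, so that value must be defined first.

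**12.2.** State that this model is the intent-to-treat analysis.

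**5.2.** Provide for the baseline CTs of participants without a week-9 scan to be read in the same blinded random sequence.

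**Secondary and sensitivity analyses.** Keep the complete-pair paired t-test as secondary. Add a sensitivity analysis for loss that depends on the unobserved week-9 value, for example no change, or a range of shifts, for those without that scan.

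**Cost.** Wording in three sections, a few lines of code in the SAS or SPSS listed in 25.1, and about 10 more existing baseline scans to read. No extra participants, scans or radiation. The model assumes that loss is explained by observed data; the sensitivity analysis probes that assumption but cannot verify it.
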